10.2 Causal Relationship of AE to Study Medication

The causal relationship of the adverse event to the study medication will be assessed as one of the following:

Unrelated:

- does not follow a reasonable temporal sequence following administration of the treatment drug

Unlikely:

- could readily be produced by other medication administered to the patient or other, environmental factors the patient has been exposed to
- has previously been causally related to other drugs the patient is taking
- does not follow a normal response pattern to the treatment drug

Possible:

- follows a reasonable temporal sequence following administration of the treatment drug

Probable:

- follows a typical temporal sequence following administration of the treatment drug

Definite:

- follows a known pattern of response to the treatment drug

10.3 Toxicity Attribution and Dose Reduction

Study medication will be held then restarted for grade 3 or 4 toxicities as outlined in the table below. If the patient experiences grade 3 toxicity on the

lowest doses, the patient will be taken off agent. There will be no dose escalation after dose reduction. Patients will not be taken off agent permanently if the SAE is clearly unrelated to the study medication. Dose reduction or stopping drug is also an option for grades 1 and 2 toxicities, irrespective of attribution to the study medication, that are unacceptable to the participant or physician.

Toxicity Attribution

Grade of Toxicity	Is Toxicity Associated with Drug Treatment				
	Unrelated	Unlikely	Possibly	Probably	Definitely
Grade 0	C	C	C	C	C
Grade 1	C	C	C	C	C
Grade 2	C	C	C	C	C
Grade 3	S-R ⁰	S-R ⁰	S-R ⁻¹	S-R ⁻¹	S-R ⁻¹
Grade 4	S-R ⁰	S-R ⁰	W	W	W

C = Continue drug

S-R⁰ = Stop drug until toxicity reaches grade 1 or lower, then restart drugs at the same doses

S-R⁻¹ = Stop drug until toxicity reaches grade 1 or lower, then restart drug at the next lower dose level (100 mg QD for erlotinib). The most common adverse events associated with erlotinib are rash (the most frequent) and diarrhea. If these adverse events do not resolve after the initial dose reduction, second dose reductions of erlotinib to 50 mg po QD are acceptable. After the second dose reductions, no further reductions will be permitted and patients with returning toxicities will be removed from the study.

W = Withdraw from trial

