7.3.1 Study medication dispensed

7.3.2 Pill diary and instructions dispensed

7.4 On-Study Evaluations (Active Treatment Period)

7.4.1 Months 1-3 (within +/- 7 days) clinic visits at months 1 and 3 to include full physical examination, examination of the oral cavity, hematology and chemistry, smoking status, alcohol usage, blood for biomarker assays and plasma trough levels (at month 3 visit), concomitant medication review, adverse event and symptom assessment, return of completed pill diaries and unused medication returned, new medication and pill diaries dispensed. For patients with visible oral leukoplakia lesions, quantitation of lesions, bidimensional measurements, and biopsy will be obtained at month 3. For patients with no visible oral leukoplakia lesions, a biopsy will be obtained at the site of the previous lesion biopsy or at mucosa adjacent to cancer resection at month 3.

7.4.2 Months 4 – 11 (within +/- 14 days) clinic visits at months 6 and 9 to include full physical examination, examination of the oral cavity, hematology and chemistry, smoking status, alcohol usage, blood for biomarker assays and plasma trough levels (at month 6 visit), concomitant medication review, adverse event and symptom assessment, return of completed pill diaries and unused medication returned, new medication and pill diaries dispensed.

- 7.4.3 Month 12 (within +/- 14 days) or Early Termination to include full physical examination, examination of the oral cavity, hematology, chemistry, smoking status, alcohol usage, blood for biomarker assays and plasma trough levels, concomitant medication review, adverse event and symptom assessment, return of completed pill diaries and unused medication. For patients with visible oral leukoplakia lesions, quantitation of lesions, bidimensional measurements, and biopsy will be obtained. For patients with no visible oral leukoplakia lesions, a biopsy will be obtained at the site of the previous lesion biopsy or at mucosa adjacent to cancer resection.
- 7.5 Follow-up (End of the active treatment period until patients are placed off study)
- 7.5.1 Every six months (within 60 days): Full physical examination, examination of the oral cavity, smoking status, alcohol usage, hematology, chemistry, blood for biomarker assays (at months 24 and month 36) and symptom assessment.

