- 7.5.2 Final visit: Full physical examination, examination of the oral cavity, smoking status, alcohol usage, hematology, chemistry, blood for biomarker assays, symptom assessment and epidemiological/nutrition questionnaires.

- 7.6 Long-term Follow-up (continued evaluation from initial participation until after the study is completed)

All patients who signed a written informed consent document (or their family members/designees), even if they were not subsequently randomized to one of the treatment arms for any reason, may be contacted by the research team (during clinic visits, by telephone, in writing, by electronic mail or by other method of communication) to confirm or provide clinical information on long-term follow-up. Participants' medical records may also be reviewed to obtain long-term follow-up information. This will allow for a better estimation, for example, of rates of invasive cancer in patients whose lesions harbor LOH or not.

- 7.7 Methods for Clinical Procedures
Clinical Investigation of Oral Cavity

Examination of the oral cavity will be conducted at each scheduled clinic visit. Leukoplakias that have increased in size or new leukoplakias will be biopsied at the discretion of the investigator. Leukoplakias will be monitored at each scheduled clinic visit and bi-dimensional measurements of the visible lesions will be performed as indicated on the study schema and study schedule of events (section 7).

Epidemiological Data

Baseline and follow-up epidemiologic and nutrition data will be collected by means of a structured questionnaire. Participants at M.D. Anderson Cancer Center will have the questionnaire administered during a 90-minute interview. All interviewers will be trained on specific interviewing techniques concerning the questionnaire, as well as general interviewing techniques (including leading and probing) to ensure accuracy and consistency of collected data.

Five percent of interviews will be re-conducted by a trained back-up interviewer to confirm consistency of collected data. Quality assurance/quality control will be assured by coding the data and removing all personal identifiers; keying coded data into a single password-protected database; utilizing a data edit check program; and by storing hard copies from all recruitment sites at M. D. Anderson Cancer Center.

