8.3 Off Agent Criteria

Patients who have been included may discontinue the study agent for general reasons (Declaration of Helsinki) or for safety reasons. A patient has the right to discontinue the study agent without having to give an explanation and without any negative effect on further treatment.

All participants discontinuing the study agent prior to normal completion (normal completion will be defined as 12 consecutive months from study treatment initiation) will be asked to return to the study site for all remaining clinic visits and follow-up visits according to the schedule of events (Section 7.1), except for patients discontinuing treatment due to diagnosis of oral cancer.

Patients may stop taking study medications for the following reasons:

- Completed the protocol-prescribed intervention
- Adverse event or serious adverse event that is unacceptable to the patient or physician
- Repeated grade 2 or greater toxicities or grade 4 toxicity that is believed to be possibly, probably or definitely related to study medication
- Disease progression requiring alternative therapy in the opinion of the Principal Investigator

- Pregnancy
- Inadequate agent supply
- Allergic reaction to the study medication(s)
- Noncompliance
- Patient desire to stop taking medication
- Concomitant medications or medical contraindications.

Patients may resume treatment if the following criteria are met:

- Patients are within the normal treatment period (i.e. within 12 consecutive months from treatment initiation)
- The reason for treatment discontinuation was not a grade 4 toxicity determined to be possibly, probably, or definitely related to the study treatment, or diagnosis of oral cancer
- There is no other reason for withholding the study treatment in the Principal Investigator's opinion

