8.4 Off-Study Criteria

Patients may go off-study for the following reasons:

- The protocol intervention and any protocol-required follow-up period is completed
- Diagnosis of cancer
- Lost to follow-up
- Withdraw consent
- Death.

Patients that have been placed off study will be asked to return to the study site for an early termination visit according to the schedule of events (Section 7.1).

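### Section 10.3 withdraws two toxicity groups from the trial while Section 8.3 keeps such patients in follow-up, so primary-endpoint censoring could depend on treatment arm

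*Combined protocol and SAP*

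**What the plan says.** Section 10.3 gives two instructions that take a patient out of the trial, not merely off the drug. Grade 4 toxicity judged possibly, probably or definitely related carries the code "W = Withdraw from trial". For toxicity that persists through dose reduction, the rule is "After the second dose reductions, no further reductions will be permitted and patients with returning toxicities will be removed from the study". The same section handles grade 3 toxicity at the bottom of the dose ladder differently: "lowest doses, the patient will be taken off agent".

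Section 8.3 lists "Repeated grade 2 or greater toxicities or grade 4 toxicity that is believed to be possibly, probably or definitely related to study medication" among the reasons to stop medication. Everyone who stops the agent early "will be asked to return to the study site for all remaining clinic visits and follow-up visits according to the schedule of events", with a diagnosis of oral cancer as the only exception. Section 8.4 lists the off-study reasons: follow-up completed, cancer, loss to follow-up, withdrawn consent and death. Toxicity is not among them.

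Once a patient is off study, little is scheduled. Section 7.5 defines follow-up as "End of the active treatment period until patients are placed off study". Section 8.4 adds one contact: "Patients that have been placed off study will be asked to return to the study site for an early termination visit". Section 7.6 says patients "may be contacted by the research team" for long-term information and allows review of medical records.

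Section 12.2 defines the primary endpoint as time to histologically confirmed oral cancer, analysed as randomized. It names refusal and death from other causes as grounds for censoring, and assumes 10% loss, uniform in time, with no difference between arms.

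**The concern.** The protocol separates off agent (8.3) from off study (8.4) and gives them different consequences. Section 10.3 crosses that line for patients whom 8.3 would keep. The primary endpoint depends on oral examinations at scheduled visits, so ending the visits ends planned ascertainment.

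The trigger is drug-related toxicity, and 10.3 names rash and diarrhea as the most common erlotinib effects. Removals would therefore probably concentrate in the erlotinib arm. Analysis by randomized arm keeps these patients in their group but does not supply cancers that nobody looked for. If the patients removed differ in cancer risk from those who stay, the censoring is informative and acts mainly on one arm. Section 12.2 does not say how such patients are analysed.

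**Working it through.** **1. The instructions side by side**

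| Situation | Section 10.3 | Sections 8.3 and 8.4 |
|---|---|---|
| Related grade 4 toxicity | Out of the trial | Off agent, all visits continue; not an off-study reason |
| Toxicity returning after second reduction | Out of the study | Repeated grade 2 or higher is an off-agent reason; not an off-study reason |
| Grade 3 on lowest dose (overlaps the row above) | Off agent | Off agent, all visits continue |

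**2. Follow-up at stake.** With 2-year accrual and analysis at 4.5 years, potential follow-up is 2.5 to 4.5 years, mean 3.5 if accrual is uniform. A patient removed midway through year 1 loses about 3.5 − 0.5 = 3 years.

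**3. The plan's own figures (Section 12.2)**
- Hazards: −ln(0.35)/3 = 0.3499 and −ln(0.61)/3 = 0.1648. Ratio 0.471, as stated.
- Simulation of 10,000 trials: 100 + 50 patients, the stated hazards, 10% uniform loss, stratified log-rank, looks at 2.5, 3.5 and 4.5 years at 0.0005, 0.014 and 0.045. A 60/40 site split is assumed. Power is 85.6% with 68.8 events, so the stated 85% reproduces.
- Check by Schoenfeld's formula at the final level: √68.8/2 × |ln 0.4709| − 2.005 = 3.123 − 2.005 = 1.118, giving power of 86.8%.

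**4. Removal unrelated to risk.** The removal rate is an assumption: 5, 10 or 20% of the 75 erlotinib patients (3.75, 7.5 or 15), spread evenly over the 12 treatment months, with no outcome recovered and none removed on placebo.

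Cancers missed at 20%, taking 10 prior-cancer and 5 IEN-alone patients removed at 0.5 year and 3 years lost:
- Prior cancer: 10 × exp(−0.1648 × 0.5) × [1 − exp(−0.1648 × 3)] = 10 × 0.921 × 0.390 = 3.6
- IEN alone: 5 × exp(−0.0676 × 0.5) × [1 − exp(−0.0676 × 3)] = 5 × 0.967 × 0.184 = 0.9

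The total is about 4.5 before the general 10% loss. The three-look simulation gives 68.8 − 64.5 = 4.3. At 5 and 10% removal it gives 1.0 and 2.2.

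Power at the final look alone (two-sided 0.045, 20,000 trials per scenario, hazard unchanged after removal):

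| Removed | Followed | Censored |
|---|---|---|
| 5% | 86.0% | 85.2% |
| 10% | 85.5% | 83.9% |
| 20% | 85.8% | 81.7% |

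The hazard ratio stays at about 0.47.

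**5. Removal related to risk, no drug effect.** Removed patients are assumed to have twice or half the others' hazard. The same share of placebo patients carries that hazard but is not removed, so the true hazard ratio is 1.00.

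| Removed | Twice: HR, rejection | Half: HR, rejection |
|---|---|---|
| 5% | 0.98, 5.0% | 1.02, 4.8% |
| 10% | 0.95, 4.9% | 1.05, 5.1% |
| 20% | 0.91, 6.5% | 1.11, 6.7% |

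With the same patients followed, the hazard ratio is 0.998–1.002 and rejection 4.4–4.7% (Monte Carlo SE 0.15–0.18 points; nominal 4.5%). If all removals fall in the first 6 months, 10–20% removal gives 0.94–0.89 or 1.06–1.12, with rejection of 5.2–7.5%. At 2% removal the hazard ratio is 0.99–1.01 with no visible inflation.

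**6. Removal related to risk, planned effect present.** Three looks, 5,000 trials per run, with the erlotinib arm's mean hazard held at the plan's value. At 20% removal of half-hazard patients, the hazard ratio is 0.52 and power 74%, against about 0.47 and 86% with follow-up. At 20% removal of double-hazard patients, they are 0.43 and 91–92%, against 0.46 and about 87%.

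**The case against.** The strongest reply is that the documents, read together, favour continued follow-up. Section 8.3 is the governing section on stopping the agent and has one exception, which is not toxicity. Its criteria for resuming treatment describe related grade 4 toxicity as a reason the drug was stopped that bars a restart, which fits code W read as a dosing instruction. The other codes in the 10.3 table all concern the drug. Section 11 asks for every reasonable effort to keep patients participating.

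Outcomes may also be recoverable. The endpoint is histological, Section 7.6 allows record review, and Section 4.4 says surgeons at the lead centre, where most patients are to be accrued, follow prior-cancer patients over the years. Those patients are 100 of the planned 150.

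Finally, the calculations stack adverse assumptions: every site follows 10.3, nothing is recovered, only erlotinib patients are removed, and the removals come on top of a 10% loss that in 12.2 already includes early drop-out. The two groups may be small, and nothing in the documents supports a doubled or halved hazard.

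Much of this stands. Continued follow-up is the likely intent, and the effect may lie at the low end of the range. It does not cancel an explicit instruction to withdraw. The wording in 7.6 is permissive, 12.2 does not say that recovered outcomes enter the primary analysis, and the 10% allowance makes no provision for a difference between arms.

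**Conclusion.** The concern holds. The current text gives conflicting instructions for two toxicity groups, and the literal reading of 10.3 stops scheduled cancer ascertainment on a trigger related to treatment. It should be fixed; confidence is medium because the size cannot be determined from the documents.

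Loss of power alone is modest, at most about 4 points with 20% of the erlotinib arm removed. Bias requires removal to be related to cancer risk. It favours erlotinib if those removed are at higher risk and works against it if they are at lower risk. It is negligible at 2% removal, small at 5–10% spread over the year, and material at about 20% or when removals come early. All removal rates and hazard multiples are assumptions, and the result also depends on which section sites follow and how much Section 7.6 recovers. The stated 85% power is not in error.

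**What to change.** In Section 10.3, replace both removal instructions with: *permanently discontinue study agent; continue all visits and oral cancer ascertainment under Sections 7.1, 7.5 and 8.3*. In Section 12.2, add that stopping the agent for toxicity is not a censoring event. For any patient already removed under 10.3, obtain cancer status through Section 7.6 and report the number by arm.

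The rules for holding, reducing and stopping the drug stay as they are. The cost is a wording amendment with sponsor, NCI and IRB approval, plus outcome retrieval for anyone already removed. No visits are added, because 8.3 already requests them.

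### The dose-reduction key in Section 10.3 takes some toxicity patients off the trial, while Sections 8.3 and 8.4, and 10.3's own opening paragraph, stop only the drug: a minor wording conflict with a two-phrase fix

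*Combined protocol and SAP*

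**What the plan says.** **Section 10.3.** In the attribution table, grade 4 toxicity that is possibly, probably or definitely related is coded W, and the key reads "W = Withdraw from trial". The S-R⁻¹ entry ends: "After the second dose reductions, no further reductions will be permitted and patients with returning toxicities will be removed from the study". The opening paragraph of the same section points the other way: a patient with grade 3 toxicity on the lowest dose comes off the agent, and nothing is said about leaving the study.

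**Section 8.3 (off agent).** The reasons for stopping medication include "Repeated grade 2 or greater toxicities or grade 4 toxicity that is believed to be possibly, probably or definitely related to study medication". Those who stop early "will be asked to return to the study site for all remaining clinic visits and follow-up visits according to the schedule of events", "except for patients discontinuing treatment due to diagnosis of oral cancer". One condition for restarting is "The reason for treatment discontinuation was not a grade 4 toxicity determined to be possibly, probably, or definitely related to the study treatment", so the lasting consequence of that event is a bar on the drug.

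**Section 8.4 (off study).** The listed reasons are completion, a cancer diagnosis, loss to follow-up, withdrawal of consent and death. Toxicity is not among them. "Patients that have been placed off study will be asked to return to the study site for an early termination visit".

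**Section 7.5.** The follow-up period is headed "Follow-up (End of the active treatment period until patients are placed off study", so being placed off study ends the six-monthly examinations.

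**Section 12.2.** Analysis is by intent to treat. The censoring sentence names refusal and death from other causes; it does not mention toxicity.

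**The concern.** The protocol has separate headings for off agent and off study, and they lead to different follow-up. After a related grade 4 event, a site using 8.3 examines the mouth at every remaining visit. A site using the 10.3 key has one early termination visit and no scheduled examination after it. That visit includes an oral examination and a biopsy, so a cancer already present can be found, but later ones depend on Section 7.6, where contact and record review are optional. Five centers use the protocol, and the 10.3 table is what a clinician is likely to consult when a grade 4 event occurs.

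Oral cancer is the primary endpoint, and removal would be triggered by drug-related toxicity. It should therefore fall mainly on erlotinib, although attribution is made blinded and some placebo patients would be removed too. That gives arm-dependent loss of follow-up in an analysis meant to follow everyone as randomized.

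**Working it through.** **1. Do the two rules cover the same patients?**

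| Event | 10.3 key | 10.3 opening | 8.3 | 8.4 |
|---|---|---|---|---|
| Related grade 4 | off trial | not addressed | off agent, visits kept | not listed |
| Toxicity returning after second reduction | off study | grade 3 on lowest dose: off agent | repeated grade 2 or greater: off agent, visits kept | not listed |

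They do, and 10.3 disagrees with itself on the second row.

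**2. The plan's own figures (Section 12.2).**
- Prior-cancer hazards: −ln(1−0.65)/3 = 0.3499 and −ln(1−0.39)/3 = 0.1648, ratio 0.471.
- IEN-alone hazards: −ln(1−0.35)/3 = 0.1436; 0.1436 × 0.471 = 0.0676; three-year rate 1−exp(−3×0.0676) = 18%.
- Power: simulation with 100 + 50 patients, 2-year uniform accrual, looks at years 2.5, 3.5 and 4.5 at levels 0.0005, 0.014 and 0.045, 10% uniform loss, and a log-rank test stratified by cancer history gives 86.0% with about 69 events. The stated 85% reproduces.

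**3. Assumptions added, because the documents give no removal rate.** Of the 75 erlotinib patients, 2%, 5% or 10% (1.5, 3.75 or 7.5), and 1% of placebo patients, stop for toxicity at a uniform time in months 1 to 6. Every site follows the key, and nothing is recovered under 7.6. These removals come on top of the 10% loss, which overstates total loss because 12.2 counts early drop-out inside that 10%. 'Kept' follows patients to year 4.5; 'removed' censors them at stopping.

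**4. Uncounted erlotinib-arm cancers, by hand.** Mean potential follow-up is 4.5 − 1 = 3.5 years and mean stopping time is 3.5/12 = 0.29 years. Patients lost to follow-up lose about half their time, a factor of about 1 − 0.10 × 0.5 = 0.95.
- *Benefit persists.* P(cancer after stopping) = exp(−0.29λ) − exp(−3.5λ). Prior cancer: 0.953 − 0.562 = 0.391. IEN alone: 0.980 − 0.789 = 0.191. Weighted 2/3 and 1/3: 0.325; × 0.95 = 0.308. Times 1.5, 3.75 and 7.5: **0.46, 1.16, 2.31**.
- *Benefit ends at stopping (control hazard afterwards).* Prior cancer 0.643, IEN alone 0.362; weighted 0.549; × 0.95 = 0.522. Times the same counts: **0.78, 1.96, 3.91**.

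Full simulation gives 0.46, 1.14, 2.29 and 0.79, 1.96, 3.89. The erlotinib-arm totals are about 25.8 and about 39 cancers.

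**5. Hazard ratio and power (stratified Cox, 2,000,000 simulated patients per arm; power from 20,000 trials of 150, single final test at 0.045).**

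| Removed | HR kept / removed, benefit persists | HR kept / removed, benefit ends for all at stopping (month 12 for completers) | Power kept / removed, benefit persists |
|---|---|---|---|
| 2% | 0.472 / 0.472 | 0.788 / 0.785 | 85.9% / 85.4% |
| 5% | 0.470 / 0.470 | 0.792 / 0.784 | 85.8% / 84.7% |
| 10% | 0.470 / 0.470 | 0.798 / 0.782 | 86.3% / 84.1% |

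Bias when benefit ends: 0.003, 0.008, 0.016, favoring erlotinib. A three-look simulation with removals spread over the treatment year and none on placebo gave 86.0% power at 5% and 84.3% at 10%.

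**6. Scale.** With about 82 events in the second scenario, the standard error of the log hazard ratio is about 2/√82 = 0.22. The bias is then ln(0.788/0.785)/0.22 ≈ 0.02 to ln(0.798/0.782)/0.22 ≈ 0.09 of one standard error. If 7.6 recovers half of the removed patients, the bias falls to 0.0015, 0.004 and 0.008.

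**The case against.** The best defense is that W is loose wording for permanent loss of drug. The other key entries are drug actions (continue, stop and restart), 10.3's opening paragraph speaks of coming off the agent, and 8.3, 8.4, Section 11 (which asks for reasonable effort to keep patients participating) and 12.2 all favor continued follow-up. This largely stands as a reading of intent. It does not remove the conflict: the words say trial and study, the protocol gives those words a consequence, and nothing says that 8.3 overrides 10.3.

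The second defense is that outcomes would be recovered anyway. Section 4.4 says surgeons at the lead center follow its prior-cancer patients for years, and that center expects to enroll the majority; prior-cancer patients are 100 of the 150. Zero recovery is therefore pessimistic. It still guarantees nothing, and the statement does not cover the other four sites.

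Two stronger readings are tempting. A reader might infer that the design itself withdraws toxicity patients and censors them at that point. The documents do not support this: 8.3 and 8.4 already choose follow-up off drug, and 12.2 does not make stopping for toxicity a censoring event. A reader might also infer material bias or a false-positive risk. No removal rate is given, and the computed effects are small. A 20% removal rate would give a bias of 0.033 if benefit ends at stopping, but nothing in the documents supports that rate. Removal was simulated as unrelated to prognosis within arm, so if erlotinib has no effect it creates no bias. Removal related to prognosis was not modeled.

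**Conclusion.** The inconsistency is real and is in the current text, between 10.3 and Sections 8.3 and 8.4, and within 10.3. Followed literally, the key would lose primary-endpoint follow-up, mainly on erlotinib, against the intent-to-treat plan. For 2% to 10% removal the cost is about 0.5 to 2.3 uncounted cancers, no hazard-ratio bias and up to about 2 points of power if benefit persists, as 12.2 implies by applying one hazard ratio to all follow-up. If benefit ends at stopping, it is about 0.8 to 3.9 uncounted cancers and a bias of about 0.003 to 0.016 favoring erlotinib. These figures rest on assumed rates, every site following the key, and no recovery under 7.6. The point is minor, and worth correcting because the loss is avoidable in a trial expecting about 69 events.

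**What to change.** Make two edits in Section 10.3:

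1. Replace "W = Withdraw from trial" with: *W = Permanently stop study agent; the patient stays on study and continues all visits under Section 8.3.* This matches 8.3, which already bars restarting after related grade 4 toxicity.
2. At the end of the S-R⁻¹ entry, replace removal from the study with: *will be taken off agent and continue all visits under Section 8.3.*

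Section 12.2 needs no change. If the sponsor wants the point stated there, limit it to: *Stopping study agent for toxicity is not a censoring event; follow-up continues until an off-study criterion in Section 8.4 is met.* A sentence promising follow-up to the end of the study without that limit would conflict with 8.4 for patients who later withdraw consent or are diagnosed with another cancer.

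The cost is two phrases. Dose rules, sample size and test levels stay as they are, and no visits are added beyond those 8.3 already requests.
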